9.2.1 Treatment-Emergent Adverse Events

Treatment-emergent adverse event (TEAE) is defined as any AE with the onset on or after the date (and time, if known) of the first study treatment. A TEAE will be considered a treatment-

emergent serious adverse event (TESAE) if it is a TEAE that additionally meets any SAE criterion.

All AEs will be included in a listing. Only TEAEs will be included for summaries, unless otherwise specified. Subjects with any TEAEs, TESAEs, severe TEAEs, TEAEs related to study treatment, TEAEs related to study procedure, TEAES related to device, TEAEs leading to study discontinuation, TEAEs leading to death, TESAEs related to study treatment, TESAEs related to study procedure, TESAEs related to device, TESAEs leading to study discontinuation, and TESAEs leading to death will be summarized.

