### 4.3 Safety

All adverse events (AEs) including injection site reactions (ISRs) will be collected from when the ICF is signed through to the last study visit (V7). Serious adverse events (SAEs) will be reported within the specified time and format directly to the Sponsor as described in Section 10.5.

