### 10.2 Medical Device Adverse Events

An AE from a medical device is defined as any undesirable physical, psychological or behavioral effect experienced by a subject during his/her participation in a study, in conjunction with the use of the device, whether or not considered related to the procedure or the product. Adverse events may include, but are not limited to, subjective or objective symptoms spontaneously offered by the subject, solicited via subject interviews, uncovered by review of concomitant medications, therapies, and treatments, and/or observed by the investigator. The investigator will record the description (sign, symptom and diagnosis), location, onset, resolution, seriousness, severity, cause, and action taken for any event on the AE eCRF.

Disease signs and symptoms that existed prior to the study injections are not considered AEs unless the condition recurs after the subject has recovered from the pre-existing condition or the condition worsens in intensity or frequency during the study.

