## 10.7 Assessment of Adverse Events

### 10.7.1 Severity

Assessment of severity of an AE will be rated according to the definitions in [Table 10.1](#) and the worst grade documented. The investigator will review these [definitions](#) with the subject for use when completing the subject diary. For events reported on the AE eCRF, e.g., ISRs that persist beyond the diary period and other AEs, the investigator will determine the severity classification based on these definitions, his/her experience in the use of dermal fillers and/or the subject's description of the event.

The term “severe” is used to describe the intensity of an AE; the event itself could be of relatively minor clinical significance (e.g., “severe headache”). This is not the same as “serious.” Seriousness of AEs is based on the outcome of an AE and usually associated with events that pose a threat to a subject’s life or functioning.

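### The SAP's TEAE definition has no worsening clause and no dating rule, so a pre-treatment AE that worsens after injection may be missing from the TEAE and TESAE summaries

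*SAP*

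**What the plan says.** SAP 9.2.1 (Treatment-Emergent Adverse Events) states that a TEAE is "defined as any AE with the onset on or after the date (and time, if known) of the first study treatment". A TESAE is a TEAE that also meets a seriousness criterion. The same section adds: "Only TEAEs will be included for summaries, unless otherwise specified". It also says: "All AEs will be included in a listing". Every AE table named in the rest of SAP 9.2 is a TEAE or TESAE table.

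Protocol 4.3 and Protocol 10 start AE collection at consent. Protocol Table 6.1 places screening between Day -14 and Day -1 and allows it to be combined with V1.

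Protocol 10.2, on device AEs, says that signs and symptoms present before the injections are not AEs "unless the condition recurs after the subject has recovered from the pre-existing condition or the condition worsens in intensity or frequency during the study". Protocol 10.7.1 asks for severity to be rated by Table 10.1 "and the worst grade documented".

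SAP 9.2 imputes mild severity when it is missing for an AE that occurred before first treatment, and says that imputed severities feed the incidence summary.

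**The concern.** A treatment-emergent summary should capture what appeared or got worse after study product. The SAP rule captures only what appeared. If an AE opened between consent and first treatment is later updated on the same record, its onset stays before Day 1. It then fails the TEAE test whatever grade it reaches and whatever causality the investigator assigns. If it becomes serious it is not a TESAE either, because a TESAE must first be a TEAE.

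For such records the error runs one way: post-treatment deterioration can be omitted but not added. The rows for any, severe, related and serious events all rest on the same definition. Two sites that see the same clinical course could also produce different counts, depending on whether they update the old record or open a new one.

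**Working it through.** The documents give no AE rate and no target figure for this point, so there is nothing to reproduce. The check is a reading of the rules against one hypothetical course, followed by a statement of scale.

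**Step 1. Can such records exist?** Yes. AEs are recorded from consent (Protocol 4.3 and 10), and the window from screening to Day 1 is at most 14 days (Protocol Table 6.1). SAP 9.2 expects such records, since it has a severity imputation rule for them. The window is zero days where V0 and V1 are combined. An event starting after the first filler but before BOTOX is already a TEAE.

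**Step 2. One course, three ways to record it.** Take a mild headache starting on Day -3 that becomes severe after injection on Day 1.

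| Recording | Basis in the documents | Onset date held | TEAE under SAP 9.2.1? |
|---|---|---|---|
| One record, grade updated | AEs recorded from consent; worst grade documented (Protocol 10.7.1) | Day -3 | No; listing only |
| AE exists only once the condition worsens | Protocol 10.2 | Date of worsening | Yes |
| Second record opened at worsening | Not stated, not forbidden | Date of worsening | Yes |

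The same clinical event is counted in two cases and not in the third. Neither document says which applies.

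**Step 3. Internal consistency.** SAP 9.2 assigns a severity to pre-treatment AEs for use in an incidence summary. SAP 9.2.1 limits summaries to TEAEs unless otherwise specified, and SAP 9.2 names no other AE summary. The imputed value therefore has no table to enter.

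**Step 4. Was this a declared change?** Protocol 11.5 calls for treatment-emergent AEs to be summarised but does not define them. SAP Appendix C does not address the definition. SAP 9.2.1 is the only operative rule.

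**Step 5. Scale.** One subject of the planned 60 is 1/60 = 1.7 percentage points; if only 48 were treated it would be 1/48 = 2.1 points.

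The number affected needs two rates that the documents do not give: p, the proportion with an AE between consent and Day 1, and w, the proportion of those that worsen after treatment. Assumed values only:

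- Expected subjects = 60 × p × w; chance of at least one = 1 − (1 − p × w)^60.
- p = 1%, w = 10%: 60 × 0.01 × 0.10 = 0.06 subjects; chance 6%.
- p = 5%, w = 25%: 60 × 0.05 × 0.25 = 0.75 subjects; chance 53%.
- p = 10%, w = 50%: 60 × 0.10 × 0.50 = 3.0 subjects; chance 95%.

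These figures apply if every worsening stays on its original record. The spread shows that the result is set by the assumptions, so it should not be read as an estimate.

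**The case against.** The strongest case against is that Protocol 10.2 makes the worsening itself the AE, so its natural onset is the date of worsening. That date falls after first treatment, and the event is counted. On that reading the protocol and SAP agree. The worst-grade instruction in Protocol 10.7.1 does not forbid a second record, and the SAP's tables by SOC and PT foresee more than one AE with the same preferred term in one subject. A condition that resolved and came back would be a recurrence with a new onset. The window is short.

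Much of this stands. A reader might infer that these events are always left out of every safety table; the documents do not support that. The omission depends on a recording convention that they do not give. The event stays in the all-AE listing. The diary-based injection site tables (SAP 9.5), the device deficiency table (SAP 9.8) and the discontinuation reasons (SAP 5.0) do not use the TEAE filter. A reader might also infer that the SAP contradicts a protocol definition of TEAE; the protocol gives none.

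The objection does not remove the gap. An event that starts after consent is also an AE from its start under Protocol 4.3 and 10, and asking for the worst grade suggests, without requiring, one record that is updated. Both readings are open, and the SAP does not choose between them.

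**Conclusion.** The point holds in a conditional form. SAP 9.2.1 selects TEAEs by onset alone. A pre-treatment AE that worsens or becomes serious after injection may therefore be absent from all TEAE and TESAE summaries if it is kept on its original record. Whether that happens turns on site recording practice, which the documents leave open.

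The size is unknown and probably small: the window is at most 14 days and can be zero, and each subject is 1.7 percentage points of 60. It is tempting to add that the severe or serious rows could be materially wrong. That would need the probability of worsening to that level and the expected row counts, and the documents give neither.

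No efficacy result or sample size is affected. The change is still worth making, because it is cheap and the possible error is an undercount of harm.

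**What to change.** 1. Extend the TEAE definition in SAP 9.2.1 with: *or any AE with earlier onset that worsened in severity or frequency, or became serious, on or after the first study treatment*. Apply the same to TESAEs.
2. State how a worsening is captured. Either a post-treatment worsening of a pre-treatment AE is entered as a new record with its own onset date, or it is flagged with a worsening date at data review before lock. The clause alone is not enough: the AE fields listed in Protocol 10.2 include no worsening date, so a single worst-grade record may not show when the change occurred. SAP 13.0 shows that data had already been collected by the March 2024 revision, so for existing records the flag at data review is likely to be the practical route.
3. Reconcile the pre-treatment severity imputation in SAP 9.2 with the TEAE-only rule: name the summary in which the imputed value is used, or delete the rule.

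The cost is a short amendment to the SAP text and a review of AE records with onset before Day 1, with source checks where the timing of worsening is unclear. The TEAE count may rise slightly.

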9.2.2 Adverse Event Overview

Overall summaries of TEAEs will include:

- The number and percentage of subjects with any TEAE
- The number and percentage of subjects with any TESAE
- The number and percentage of subjects with any severe TEAE
- The number and percentage of subjects with any TEAE related to JUVÉDERM VOLITE
- The number and percentage of subjects with any TEAE related to JUVÉDERM VOLBELLA
- The number and percentage of subjects with any TEAE related to JUVÉDERM VOLIFT
- The number and percentage of subjects with any TEAE related to JUVÉDERM VOLUMA
- The number and percentage of subjects with any TEAE related to JUVÉDERM VOLUX
- The number and percentage of subjects with any TEAE related to BOTOX cosmetic
- The number and percentage of subjects with any TEAE related to study procedure
- The number and percentage of subjects with any TEAE related to device
- The number and percentage of subjects with any TEAE leading to study discontinuation

- The number and percentage of subjects with any TEAE leading to death
- The number and percentage of subjects with any TESAE related to JUVÉDERM VOLITE
- The number and percentage of subjects with any TESAE related to JUVÉDERM VOLBELLA
- The number and percentage of subjects with any TESAE related to JUVÉDERM VOLIFT
- The number and percentage of subjects with any TESAE related to JUVÉDERM VOLUMA
- The number and percentage of subjects with any TESAE related to JUVÉDERM VOLUX
- The number and percentage of subjects with any TESAE related to BOTOX cosmetic
- The number and percentage of subjects with any TESAE related to study procedure
- The number and percentage of subjects with any TESAE related to device
- The number and percentage of subjects with any TESAE leading to study discontinuation
- The number and percentage of subjects with any TESAE leading to death
 - Before BOTOX Treatment
 - On or After BOTOX Treatment

9.2.1 Treatment-Emergent Adverse Events by SOC and PT, and/or Severity

The number and percentage of subjects will be summarized by SOC and PT, and by maximum severity, SOC, and PT as follow:

- TEAEs by SOC and PT
- TEAEs by maximum severity, SOC, and PT

- TEAEs related to study treatment (JUVÉDERM VOLITE, JUVÉDERM VOLBELLA, JUVÉDERM VOLIFT, JUVÉDERM VOLUMA, JUVÉDERM VOLUX, and BOTOX cosmetic) by SOC and PT
- TEAEs related to study treatment (JUVÉDERM VOLITE, JUVÉDERM VOLBELLA, JUVÉDERM VOLIFT, JUVÉDERM VOLUMA, JUVÉDERM VOLUX, and BOTOX cosmetic) by maximum severity, SOC, and PT
- TEAEs related to study procedure by SOC and PT
- TEAEs related to study procedure by maximum severity, SOC, and PT
- TEAEs related to device by SOC and PT
- TEAEs related to device by maximum severity, SOC, and PT
- TEAEs leading to study discontinuation by SOC and PT
- TEAEs leading to death by SOC and PT

The TEAE summary tables will be presented with SOC in alphabetical order and in decreasing frequency within each SOC. If more than 1 AE is coded to the same SOC or PT for the same subject, the subject will be counted only once for that SOC or PT using the most severe occurrence for the summarization by severity.

In addition, the duration of TEAEs will be summarized by SOC and PT. The duration of a TEAE will be calculated as (AE End Date – AE Start Date) + 1, and summarized as:

- 1 – 3 Days
- 4 – 7 Days
- 8 – 14 Days
- 15 – 30 Days
- ≥ 30 Days

The duration summary table will be presented with SOC in alphabetical order and in decreasing frequency within each SOC. If more than 1 AE is coded to the same SOC or PT for the same subject, the subject will be counted only once for that SOC or PT under the maximum duration.

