## 11.5 Adverse Events

Device-related AEs will be captured with TrackWise Enterprise Quality Management Software and coded using AE term codes. Treatment-emergent AEs will also be summarized by serious AEs (SAEs), AE severity, AE leading to treatment or study early termination, and relationship to study drugs/devices and procedures. SAEs will be coded using MedDRA version 21.0 or higher and presented by system organ class and preferred term.

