9.2 Adverse Events

Adverse events (AEs) will be summarized and presented using primary MedDRA System Organ Classes (SOCs) and preferred terms (PTs).

An AE will be considered a JUVÉDERM injection related AE if it has a reasonable possibility (Possible, Probable, or Causal relationship) that the JUVÉDERM injections caused the event. The JUVÉDERM injections include JUVÉDERM VOLITE, JUVÉDERM VOLBELLA, JUVÉDERM VOLIFT, JUVÉDERM VOLUMA, and JUVÉDERM VOLUX.

An AE will be considered a BOTOX related AE if it has a reasonable possibility (Reasonable Possibility) that the BOTOX cosmetic caused the event.

An AE will be considered a study procedure related AE if it has a reasonable possibility (Possible, Probable, or Causal relationship) that the study procedure caused the event.

An AE will be considered a device related AE if it is related to a device malfunction/deficiency.

If the causal relationship to the study treatment/device/procedure is missing for an AE that occurred on or after the date of the first study treatment, then a causal relationship will be imputed for analysis. The imputed values for relationship to study treatment/device/procedure will be used for the incidence summary; the actual values will be presented in data listings.

If severity is missing for an AE that occurred before the date of first study treatment, then a severity of mild will be imputed for analysis. If the severity is missing for an AE that occurred on or after the date of the first study treatment, then a severity of severe will be imputed. The imputed values for severity will be used for the incidence summary; the actual values will be presented in data listings.

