9.2.2 SAEs (Including Deaths) and Adverse Events Leading to Study Discontinuation

An SAE is defined as any AE that:

- led to death
- led to serious deterioration in the health of the subject, that either resulted in
 - a life-threatening illness or injury; or
 - a permanent impairment of a body structure or a body function; or
 - in-patient hospitalization or prolongation; or
 - medical or surgical intervention to prevent permanent impairment to body structure or a body function; or
- led to fetal distress, fetal death or a congenital abnormality or birth defect.

TESAEs, TESAEs related to study drug, TESAEs related to study procedure, TESAEs related to device, TESAEs leading to study discontinuation, and TESAEs leading to death will be summarized in the overall summary table, and by SOC and PT as follow:

- TESAE by SOC and PT
- TESAEs related to study treatment (JUVÉDERM VOLITE, JUVÉDERM VOLBELLA, JUVÉDERM VOLIFT, JUVÉDERM VOLUMA, JUVÉDERM VOLUX, and BOTOX cosmetic) by SOC and PT
- TESAEs related to study procedure by SOC and PT
- TESAEs related to device by SOC and PT
- TESAEs leading to study discontinuation by SOC and PT

- TESAEs leading to death by SOC and PT

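### HArmonyCa Lidocaine has no relatedness definition in the SAP and no place in any product-related TEAE or TESAE table, and Appendix C does not declare this

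*SAP*

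**What the plan says.** SAP 9.2 (Adverse Events) sets out four kinds of relatedness.

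- **Juvéderm:** "The JUVÉDERM injections include JUVÉDERM VOLITE, JUVÉDERM VOLBELLA, JUVÉDERM VOLIFT, JUVÉDERM VOLUMA, and JUVÉDERM VOLUX".
- **BOTOX:** a separate definition of its own.
- **Study procedure:** "An AE will be considered a study procedure related AE if it has a reasonable possibility" that the procedure caused it.
- **Device:** "An AE will be considered a device related AE if it is related to a device malfunction/deficiency".

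The section headed Treatment-Emergent Adverse Events then promises summaries of "TEAEs related to study treatment, TEAEs related to study procedure, TEAES related to device", with no restriction by product.

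The output sections spell the products out. The overview has one row per product for TEAEs and one for TESAEs, and both sets end with BOTOX (for example "The number and percentage of subjects with any TESAE related to BOTOX cosmetic"). The SOC/PT section lists "TEAEs related to study treatment (JUVÉDERM VOLITE, JUVÉDERM VOLBELLA, JUVÉDERM VOLIFT, JUVÉDERM VOLUMA, JUVÉDERM VOLUX, and BOTOX cosmetic) by SOC and PT" and repeats the same list by maximum severity. The SAE section lists "TESAEs related to study treatment (JUVÉDERM VOLITE, JUVÉDERM VOLBELLA, JUVÉDERM VOLIFT, JUVÉDERM VOLUMA, JUVÉDERM VOLUX, and BOTOX cosmetic) by SOC and PT".

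Protocol 11.5 says treatment-emergent events will be summarized by several attributes, ending "and relationship to study drugs/devices and procedures". SAP 1.0 says changes to protocol-planned analyses are detailed in Appendix C.

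**The concern.** HArmonyCa Lidocaine is a study treatment throughout most of both documents. It is in the objectives (SAP 2.1), the treatment list (SAP 2.3), the treatment-completion summary (SAP 5.0) and the exposure summary (SAP 6.0). Protocol Appendix 8 lists it as a study device. Adding it was the stated reason for protocol Version 2, on which this SAP is based. Yet the relatedness section and the product lists read as if it were not in the study.

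At stake is the product-attributed tabulation of events recorded on the AE eCRF: events other than injection site reactions, injection site reactions lasting beyond 30 days (protocol 10.3), and any HArmonyCa-related SAE. A reader who takes a table of treatment-related events at its title would see too few of them, and would have no figure for the product the amendment brought in. The rule in SAP 9.2 that imputes a causal relationship when it is missing also has no HArmonyCa category to feed.

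**Working it through.** The plan states no figure here to reproduce. The check is a count of definitions and rows, followed by a look at whether other outputs close the gap.

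**Count of products and rows**

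Named study products: HArmonyCa, VOLITE, VOLBELLA, VOLIFT, VOLUMA, VOLUX, BOTOX = 7.

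| SAP location | Product entries | HArmonyCa |
|---|---|---|
| 9.2, relatedness definitions | 4 (Juvéderm, BOTOX, procedure, device malfunction/deficiency) | none |
| Adverse Event Overview | 6 TEAE rows + 6 TESAE rows = 12 | 0 of 12 |
| TEAEs by SOC/PT, and by maximum severity | 2 lists of 6 products | 0 of 2 |
| TESAEs by SOC/PT | 1 list of 6 products | 0 of 1 |

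Tables with product-related content: 1 overview + 2 + 1 = 4. HArmonyCa is absent from all 4.

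**Is the change declared?** Appendix C has five rows: efficacy populations, subgroups, the mITT definition, the Evaluable definition and exploratory imaging. None concerns AE relatedness.

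**Do other outputs close the gap?**

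- *Device-related rows:* limited to malfunction or deficiency, so an ordinary reaction to a correctly functioning gel does not qualify.
- *Procedure-related rows:* a separate judgement about the procedure. An event attributed to both gel and procedure is tabulated there; one attributed to the gel alone is not.
- *Device deficiencies by suspect device type (SAP 9.8):* these count deficiencies, not reactions to the product.
- *HArmonyCA / Non-HArmonyCA columns (SAP 5.0 and 9.1):* a split of subjects. Subjects in the HArmonyCA group go on to Juvéderm and BOTOX, so the split does not attribute an event to a product.
- *Diary summary (SAP 9.5):* covers injection site reactions for 30 days after each filler treatment only.

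**How long is HArmonyCa the only study product given?** Inputs are the visit windows in the schedule of activities (V2 to V5 each 30 ± 7 days after the previous visit; V6 and V7 nominally 15 days each) and its footnote 14, which sends a subject without a V2 touch-up straight to V3 activities.

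- With a V2 touch-up, V1 to V3: 30 + 30 = 60 days; range 23 + 23 = 46 to 37 + 37 = 74. Nominal total: 30 + 30 + 30 + 30 + 15 + 15 = 150 days. Share: 60/150 = 40%.
- Without a touch-up, V3 activities done at V2: 30 days; range 23 to 37. Nominal total: 30 + 30 + 30 + 15 + 15 = 120 days. Share: 30/120 = 25%.

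A product-related event with onset in that window can only be attributed to HArmonyCa, and no product row can receive it.

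**The case against.** The strongest reply is that this is an incomplete descriptive tabulation in a study whose objectives are all about efficacy. The SAP's safety endpoints are subjects with any AE, ISR or device deficiency; relatedness is not one of them. HArmonyCa events stay in the all-cause tables by SOC/PT, severity and duration, split by treatment group. They also stay in the AE listing, where actual causality values are to be shown. No test, sample size or efficacy result changes. All of this is true. It limits the harm to attribution, but it does not make a table of treatment-related events correct when one treatment is left out.

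It can also be said that protocol 11.5 names no product and promises no per-product rows. That is so. The departure follows because HArmonyCa is a study device under protocol Appendix 8, and because protocol 10.7.2 asks for a causality judgement on every study product.

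The SAP is not wholly consistent about HArmonyCa: its Evaluable Population (4.1.2) names only Juvéderm and BOTOX as the study products received. That definition governs efficacy analyses and does not justify the gap in safety.

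Three cautions stand. The day shares measure calendar time, not events. The design overview says a subject without a touch-up *may* advance, so one who does not keeps the longer window. Table specifications are in a separate document not available here, though that does not alter the lists the SAP itself gives.

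**Conclusion.** The point holds and should be corrected. The SAP defines no HArmonyCa relatedness, omits 1 of 7 named products from all 4 tables with product-related content, narrows its own unrestricted commitment to treatment-related summaries, and does not declare the departure from protocol 11.5. Followed as written, it would understate treatment-related TEAEs and TESAEs by the subjects whose only related events were attributed to HArmonyCa and to no other listed product; if those events were also not attributed to the procedure or to a malfunction or deficiency, they would appear in no relatedness table at all. The size of that understatement cannot be computed, because the documents give no event rates. No event is lost from the all-cause summaries or the listing, and efficacy is unaffected. The conclusion rests on the SAP text alone; the sections concerned carry no redaction mark.

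**What to change.** - Add to SAP 9.2 a definition of a HArmonyCa-related AE, parallel to the Juvéderm one.
- Add a HArmonyCa row for TEAEs and one for TESAEs to the overview, taking the product rows from 12 to 14 (7 + 7).
- Add HArmonyCa Lidocaine to the product lists of the three related SOC/PT tables, taking each from 6 to 7 products.

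The cost is one definition, two rows and one product name in three lists, with the matching table specifications. Sample size, power and alpha do not change.

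This assumes that the eCRF records causality for HArmonyCa. Protocol 10.7.2 requires the judgement, but the eCRF is not among the documents, so the sponsor should confirm it. If the field was not collected, add an explained row to Appendix C and state in the titles of the affected tables that HArmonyCa is not covered.
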